4.0 Research Design and Methods

Describe the research design and methods and procedures to be used in achieving the specific aims of the research project. If applicable, mention the type of personal protective equipment (PPE), use of aerosol confinement, and the need for the use BSL2 or BSL3 laboratory for different part of the intended research in the methods.. Define the study population with inclusion and exclusion criteria, the sampling design, list the important outcome and exposure variables, describe the data collection methods/tools, and include any follow-up plans if applicable. Justify the scientific validity of the methodological approach (biomedical, social, gender, or environmental).

Also, discuss the limitations and difficulties of the proposed procedures and sufficiently justify the use of them.

This study is a phase II, randomized, placebo controlled, double blind efficacy and safety trial. The study is designed for the assessment of a novel fixed dose combination (FDC) drug VR-AD-1005 for the treatment of acute watery diarrhea in adult cholera patients. Adult (18-65 years) cholera patients admitted to icddr, Dhaka Hospital will be randomized to intervention and placebo groups with 75 patients per group.

Group A (intervention product arm): Patients will receive VR-AD-1005 treatment for three days, or less if recovered earlier, in addition to the general cholera protocol treatment.

[figure not shown]
Group B (placebo arm): Patients will receive placebo for three days, or less if recovered earlier, in addition to the general cholera protocol treatment.

Key aspects of the trial design and Trial Schema are given below in table 2 and figure 2.

Table 2: Key aspects of the trial design

Intervention Model: Parallel arm intervention model with 2 Arms: Group A (intervention product arm) and Group B (placebo arm)	Population Type: [Adult patient]
Control: [placebo] Intervention: [VR-AD-1005]	Population Diagnosis or Condition: [Vibrio cholerae infection]
Active Comparator: [not applicable]	Population Age: Minimum: [18y.o.] – Maximum: [65y.o.]
Trial Intervention Assignment Method: Double-blind randomization	Site Distribution: Single site

Figure 2-Trial Schema

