4.3. Sequence of events

- All prospective patients visiting the facilities aged 18-65 years experiencing acute watery diarrhea (duration 24 hours or less) and severe dehydration will be assessed. Assessment will be done primarily by the study nurses (at least three nurses will rotate for the study duration). Study doctors will also assist with the assessment.
- Consent will be sought from suspected patients to enroll cases. Confirmatory microbiology for cholera will be done. Eligibility of the participants will be identified using the screening tool. This study will not include vulnerable participants (refer to inclusion and exclusion criteria in sections 4.2.3 and 4.2.4).
- Trained nurses/study doctors will take the patients (who fulfil all inclusion criteria and do not meet any of the exclusion criteria) or guardian for critically ill patients through the consenting process. This will involve explaining in plain language what the study is about and the risk/benefits of participating. Participants will be informed that participation in the trial is voluntary and that they can withdraw at any time during the 3 days of inpatient care. They will be required to sign applicable consent forms, one form will be kept by investigators and another will be given to participants.
- Upon consenting, randomization will be done by the independent researcher and treatment started by the study nurses in consultation and supervision by study doctors, in addition to standard management for *V. Cholerae* for patients.
- All patients will be admitted in the dedicated wards of the study site for all the 3 days of treatment. Early discharges will not be permitted for enrolled study participants due to safety and endpoint measurement reasons. To facilitate data analysis, and in particular safety analysis (development of possible adverse events, while undergoing treatment with VR-AD-1005), all

participants with different level of severity of the disease must follow the same treatment protocol. Having variations in the treatment strategy, such as early discharge, may complicate the conduct of the trial. An example of such complication is the development of unrelated AEs which stem from changes in the lifestyle of participants after discharge, for example, change in diet or a community-acquired disease, which will be prevented and avoided by having all participants as in-patients.

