4.4.4. Dosing and Administration

Cholera typically presents with voluminous liquid stool due to hypersecretion of fluids by the intestine²¹. VR-AD-1005 is not absorbed and acts at the level of intestinal mucosa. Thus, first dose of the drug is dissolved in much larger than normal volume of fluid presented in the intestine of a patient recently admitted for cholera. In addition, due to the diarrhea, first dose of the drug is evacuated with stool faster than subsequent doses. In order to maintain working concentration and counteract dilution, first dose of the drug is tripled, representing the "loading dose" drug administration tactics. The remaining doses are single doses for the three days which is in line with average duration of the cholera episode and thus gives sufficient time for the drug to exert its effect. The treatment will be administered to participants under the supervision of trained study personnel, i.e. study nurse. Nurses will be instructed to monitor for vomiting or accidental loss of treatment dose (for example, dropped dose). The participants will be instructed to swallow the treatment whole without chewing with a glass of water or oral rehydration solution. The volume of the liquid will be registered in the water intake charts.

Administration begins when the patient is able to swallow the tablet. If the patient vomits less than 30 minutes after administration of dose, the dose will have to be re-administered after about 15 minutes. If the patient vomits after 40 minutes, the clinician will check the vomitus to see if the medication is in there, if the medication is not visible then the dose is not re-administered. If the medication is visible, then the dose is re-administered after 15 minutes. Both arms will receive extra doses of the medication for these purposes. In the event of lost dose, the pharmacy will have a backup of the medication doses for emergency purposes.

VR-AD-1005 oral dose will be administered orally 4 times per day (approximately every 4-5 hours with overnight break to allow for participants rest and recovery) with first administration of 3 capsules as loading dose. Dosing is indicated in the table below (**Table 3**), with reasonable timing of administration at 7:00, 12:00, 17:00 and 21:00 hours \pm 1 hour.

Table 3: VR-AD-1005 doses and dosing schedule

Time	Day 1	Day 2	Day 3
Time 0 hr	3 doses	1 dose	1 dose
Time +5:00 hr	1 dose	1 dose	1 dose

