4.6. Start of Trial and End of Trial

Trial starts once the participant has signed the informed consent form. The end of trial is defined as database lock after completion of the study by the last patient. A participant is considered to have completed the study if he or she has completed all phases of the study including the last visit or the last scheduled procedure shown in **Appendix I**.

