4.11. Discontinuation of Trial Intervention and Participant Withdrawal from Trial

Participants may withdraw from a research study for any reason, even without mentioning any reason. The participants will be able to receive standard treatment of the hospital without any penalty. For evaluation and reporting purposes, researchers may ask participants for their reasons for early withdrawal.

An investigator may discontinue trial intervention or withdraw a participant from the study for the following reasons:

- Significant study intervention non-compliance.
- If any adverse event (AE), Serious adverse events (SAE), laboratory abnormality, or other medical condition or situation occurs, continued participation in the study would not be in the best interest of the participant.
- Disease progression which requires discontinuation of the study intervention
- If the participant meets an exclusion criterion (either newly developed or not previously recognized) that precludes further study participation.
- Participant unable to receive study intervention for 3 days.
- Reporting over-dose
- protect a participant from excessive risk or risk with a demonstrated lack of benefits (e.g., a participant experiences serious side-effect without the anticipated therapeutic effects), or
- maintain the integrity of the data (e.g., a participant is not following study procedures or may be deliberately providing false information).

Whenever an investigator terminates a subject's participation in research, the investigator must explain to the participant the reasons for the termination and, as appropriate, other treatment options available to the participant.

The data to be collected at the time of study intervention discontinuation will include the following:

- Physical examination
- Vital signs
- Complete blood count (CBC)
- Blood Basic metabolic panel, including Serum electrolytes and creatinine
- Assessment of vomiting
- Assessment of stool output
- Assessment of dehydration
- Assessment of IV and oral ORS and oral water intake
- Assessment of urine output
- Administration of questionnaires or other instruments helping participants to register symptoms, such as stool charts.
- Assessment of adverse events.

Follow-up calls will be made with patients who completed the protocol with questionnaires focusing on the side effects. Calls will be made once a week during the 28-day follow-up period.

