Number of unscheduled IV rehydration episodes per treatment. The number of unscheduled IV rehydration episodes per treatment will be recorded for the entire duration of the treatment. Unscheduled IV rehydration is defined as "receipt of IV fluid during the maintenance phase of hydration due to development of severe dehydration or some dehydration with high purging (>15 ml/kg/hour) or persistent vomiting (>3 episodes/hour), or failure to take ORS for any reason"
- Duration of IV rehydration for the entire treatment period per treatment group and per each 24-hour period of treatment.
- Number of recovered subjects within treatment group. The number of recovered subjects will be recorded as total for the entire treatment duration, and as number of recoveries per each 24-hour period of treatment.
- Safety will be measured by the proportion of patients that will present with AE following administration of VR-AD-1005.

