6.2. Analysis Supporting Primary Objectives

6.2.1. Statistical Model, Hypothesis, and Method of Analysis

Primary Endpoint:

Reduction in stool output volume over a treatment period.

Primary Endpoint 1., Hypothesis 1. Treatment with VR-AD-1005 reduces stool output in patients with diarrhea due to *V. cholerae* infection. Null hypothesis is stated as no statistically significant difference in stool output volume as compared to placebo; alternative Hypothesis 1 is stated as statistically significant reduction in stool output volume in patients treated with VR-AD- 1005.

Two analytical approaches are proposed. Approach 1 will be based on the total quantity of stool purged by participant during the intervention administration period. Stool output will be expressed as g/kg body weight based on the stool charts, and the means will be compared between intervention and placebo groups using Student's unpaired t-test. In approach 2, stool purging is measured and plotted as total stool output in ml/kg/12 hours based on the individual stool collection charts. Weight of stool will be converted to volume using 1:1 weight/volume ratio. Diarrhea of cholera resolves rapidly, and majority of patients are expected to recover within 30-50 hours after randomization. 12-hour analysis increments allow a better insight into the onset and timing of the effect of study intervention as compared to cumulative data over the duration of the treatment. Means will be compared for each 12-hour period after first intervention administration using unpaired Student's t-test. Normal distribution is assumed for both cases. Analysis will be conducted in the ITT, MITT and PP groups. Missing data and outliers will be handled using imputation technique. Non-adherence and lost to follow-up patients will be categorized into the appropriate group and handled accordingly. No subtractions will be made from the ITT group after randomization assignment.

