6.4. Safety Analyses

Safety analysis is not the primary or secondary objective of this study, thus safety will be analyzed as summary statistics during treatment. AEs will be coded per Medical Dictionary for Regulatory Activities (MedDRA), and calculated. Each AE will be counted once only for a given participant, and presented using standard available criteria for severity, frequency, and relationship of AEs to study intervention. Start date, stop date, severity, relationship, expectedness, outcome, and duration will be reported for each SAE. Adverse events leading to premature discontinuation from the study intervention and serious treatment-emergent AEs will be listed. Proportion of the patients presented with AE or SAE will be calculated for IP and Placebo arms as a fraction of the total number of participants per arm and expressed as percent. Percentage of AE and SAE occurrence will be compared between IP and placebo groups to provide information regarding the safety of the investigational product.

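### Whether study treatment ends at recovery or at 72 hours is contradictory, so exposure and the adverse-event and IV-rehydration windows are not fixed

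*Combined protocol and SAP*

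**What the plan says.** **Length of treatment.** Section 4.0 describes the active arm: "Patients will receive VR-AD-1005 treatment for three days, or less if recovered earlier, in addition to the general cholera protocol treatment". The placebo arm has the same wording, so in both arms dosing ends at recovery if that comes first.

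Other sections carry no such stop. Section 4.3 gives scheduled doses on each day of a three-day admission and rules out early discharge; in explaining that rule it says that all "participants with different level of severity of the disease must follow the same treatment protocol". Section 4.4.4 says: "The remaining doses are single doses for the three days". Table 3 and Appendix I show four administrations on each of days 1 to 3. Table 1 (Section 5.0) and Section 6.0 place the end of treatment at 72 hours.

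**Expected recovery.** Section 6.2.1 says that the "majority of patients are expected to recover within 30-50 hours after randomization". Section 6.3 puts the average duration of diarrhea at 30-35 hours.

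**Analysis windows.** Section 6.0 says: "The number of unscheduled IV rehydration episodes per treatment will be recorded for the entire duration of the treatment". Duration of IV rehydration also runs over the treatment period. Section 6.3 measures rehydration volume over the course of treatment in one sentence and over the course of the study in another. Section 6.4 says that "safety will be analyzed as summary statistics during treatment"; the proportion with an adverse event (AE) uses all participants in the arm as denominator, with no adjustment for time observed.

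**Patient status.** Section 4.6 counts a participant as complete who has "completed all phases of the study including the last visit or the last scheduled procedure shown in" Appendix I. Section 4.11 lists "Participant unable to receive study intervention for 3 days" among the reasons for which an investigator may discontinue treatment or withdraw a patient.

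**The concern.** The two descriptions of treatment length differ for the typical patient, because recovery is expected well before 72 hours. Staff following Section 4.0 would stop capsules at recovery; staff following Section 4.4.4 and Appendix I would continue through day 3. Exposure to the product would then depend on which section was read.

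The analysis inherits the ambiguity. If treatment ends at recovery, anything counted during treatment is counted over a period whose length is itself an outcome. Hypothesis 3 in Section 6.3 is that the product shortens diarrhea. If it does, active patients would be observed for AEs over a shorter time than placebo patients, and a crude percentage per arm would favour the product even with equal true AE rates.

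The final culture, bloods and examination have the same problem. They sit in an end-of-treatment column of Appendix I that has no clock time.

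**Working it through.** **The plan's own figures.** The plan gives no AE rate and no effect on duration, so it has no figure to reproduce on this point. Its power figures concern stool output and do not enter here.

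**Step 1: exposure under each reading.** Taking the Table 3 times (0, 5, 10 and 15 hours of each day, first administration tripled), administrations fall at 0, 5, 10, 15, 24, 29, 34, 39, 48, 53, 58 and 63 hours from first dose.

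| Dosing stops at | Administrations | Doses |
|---|---|---|
| 33 h | 6 of 12 | 3 + 5 = 8 of 14 |
| 50 h | 9 of 12 | 3 + 8 = 11 of 14 |
| 72 h | 12 of 12 | 3 + 11 = 14 of 14 |

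The trigger for stopping is not unique either. Table 1 defines clinical recovery by two consecutive soft stools. Table 1 and Section 6.0 end the duration of diarrhea at the first non-watery stool or 12 hours without stool. Section 6.3 uses the first formed stool or 12 hours without stool.

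**Step 2: AE proportions if the window ends at recovery.**

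- From the plan: placebo recovery at 30, 35 or 50 hours (Sections 6.2.1 and 6.3); cap at 72 hours.
- Assumed: diarrhea 10%, 20% or 33% shorter on active; AE risk over 72 hours (p72) of 10%, 30% or 50%; a constant hazard, equal in both arms.
- Hazard: h = -ln(1 - p72)/72.
- Proportion with an AE in a window of w hours: p = 1 - exp(-h × w).

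Example with p72 = 30%: h = 0.3567/72 = 0.00495 per hour.

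- Placebo, w = 35: p = 1 - exp(-0.173) = 15.9%.
- Active, w = 35 × 0.67 = 23.45: p = 1 - exp(-0.116) = 11.0%.
- Ratio = 11.0/15.9 = 0.69. With 75 per arm this is about 11.9 against 8.2 patients.

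All results for p72 = 30% and fixed recovery times:

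| Placebo window | Placebo AE | Active, 10% shorter | 20% shorter | 33% shorter |
|---|---|---|---|---|
| 30 h | 13.8% | 12.5% (0.91) | 11.2% (0.81) | 9.5% (0.69) |
| 35 h | 15.9% | 14.4% (0.91) | 13.0% (0.81) | 11.0% (0.69) |
| 50 h | 21.9% | 20.0% (0.91) | 18.0% (0.82) | 15.3% (0.70) |

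For recovery times that vary exponentially with mean m, capped at 72 hours, p = h/(h + 1/m) × [1 - exp(-72 × (h + 1/m))]. Over both forms and all three values of p72, the spurious ratio is 0.90-0.95 for 10% shortening, 0.80-0.89 for 20% and 0.67-0.80 for 33%.

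**Step 3: a fixed 72-hour window.** Both arms have w = 72, so p = p72 in each and the ratio is 1.00.

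**Step 4: which outcomes are exposed.**

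- Exposed: AE and SAE proportions, IV duration and total rehydration volume.
- Exposed in part: unscheduled IV episodes (see the objection).
- Not affected: time to recovery, which ends at recovery anyway; the count of recovered patients; and the 12-hour and 24-hour hydration analyses, whose windows are already fixed.

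The primary stool measure is not sized here. Table 1 ends it at recovery or 72 hours, whichever is earlier.

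**The case against.** The strongest reply is that the plan already means 72 hours. Table 1 and Section 6.0 treat recovery and the end of treatment as separate times and attach 72 hours to the latter. Everyone stays in hospital for three days, Appendix I schedules stool, fluid and AE assessments through day 3, Section 4.7.4 records all AEs while on study, and Section 4.11 adds weekly calls over 28 days. The safety endpoint in Table 1 and Section 6.0 counts AEs following administration, with no stop at the last dose. On this reading no window shrinks. This stands as a reading, and it shows that the data can be collected over a common window. It does not remove the conflict with Section 4.0 or say which period Section 6.4 summarises.

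Several stronger readings are tempting, and the documents do not support them:

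- **Recovered patients would be withdrawn or lost from analysis.** Section 4.11 speaks of being unable to receive treatment, under a permissive may; stopping because of recovery is not plainly covered. Completion in Section 4.6 turns on the last visit or procedure, not the last capsule. Section 4.4.6.1 does assign to arms the data of those who completed, but Section 6.2.1 allows no removals from the ITT group. What remains is that Section 6.1 defines neither the MITT nor the PP group, so the per-protocol status of an early stopper is unstated.
- **Relapse after recovery would go unseen.** The inpatient stay, the day-3 assessments and the calls contradict this.
- **Fewer IV episodes on active would be an artefact.** These episodes require dehydration, heavy purging, persistent vomiting or failure to take ORS. They belong mainly to active diarrhea, so a reduction after faster recovery is largely the treatment effect.
- **Section 4.3 itself mandates three days of capsules for all.** Its sentence on a common treatment protocol sits in a paragraph about early discharge. The stronger evidence is its scheduled daily dosing together with Section 4.4.4 and Appendix I.

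A redacted block before Section 4.4.3 and the trial schema cannot be seen, and either may address duration. The visible sections conflict regardless.

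**Conclusion.** The contradiction over when dosing ends is real and affects the typical patient: 6 to 9 of 12 administrations under one rule, 12 under the other. The AE window and several secondary windows are tied to treatment without a single stated end.

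A reader might infer that the safety comparison is biased, or that active patients would show a third fewer AEs. Neither follows. The artefact arises only if treatment is taken to end at recovery and the product does shorten diarrhea. Its size, a ratio of about 0.67-0.95, rests on a constant and equal hazard, an assumed 72-hour risk of 10-50% and an assumed 10-33% shortening. A third is the extreme of that range; the plan's own 33% refers to stool quantity, not duration. If AEs cluster in the first hours, the artefact would be smaller. If treatment means 72 hours, it is nil.

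This should be fixed before enrolment. It is an ambiguity with a conditional consequence, not a demonstrated bias.

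**What to change.** 1. The sponsor and investigators should reconcile Section 4.0, Section 4.3, Section 4.4.4 with Table 3, Table 1 and Appendix I on when study treatment ends. Which rule is right is for them to decide.
2. Whichever rule is chosen, state in Sections 6.0, 6.3 and 6.4 that in-hospital AEs, unscheduled IV episodes, IV duration and total rehydration volume are analysed over a fixed 0-72 hours from first dose, in every patient in both arms, regardless of the last dose. Report AEs also over the 28-day follow-up.
3. Reconcile the timing of the end-of-treatment assessments so that it is the same in both arms and does not depend on recovery.
4. If stopping at recovery is kept, state in Sections 4.6 and 4.11 that it is not a withdrawal, a non-completion or a per-protocol exclusion.

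The cost is protocol wording. Patients already remain in hospital for three days with assessments scheduled through day 3, and the follow-up calls are already planned. The change is needed before enrolment, because inconsistent exposure cannot be corrected afterwards.
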